Cancer remains a fatal disease that continues to kill far more patients daily than COVID-19. The need to identify better treatments through clinical research is not affected by the presence of the pandemic. Pausing such research for months, if not years, until the pandemic subsides will likely result in more deaths as improvements in care are delayed. Nevertheless we have put in place significant mitigations. The COVID-19 risk for potential patients has been minimised as much as possible. The WINGMEN recruitment site, Churchill Hospital, is nominally COVID-19 free, and infected or potentially infected patients are treated at a geographically distinct site (the John Radcliffe Hospital). The following procedures have also been put in place at site:

- All patients (in and outpatients) are screened upon entry to the Churchill site
- Human traffic at the Churchill site is minimal with face to face appointments avoided and staff working from home, whenever possible.
- Face masks/social distancing/level 1 PPE for patient examinations and other protective measures are mandatory for staff at the Churchill site

Furthermore, this trial requires only 6 extra patient visits: screening, 4 treatment visits (unless surgery is unexpectedly delayed) and one visit after completion of treatment and before surgery, for post-treatment blood tests. The post-treatment End-of-Study trial assessment will be held on the same day as the routine 6-week post-operative assessment, and so will not involve an extra hospital visit. There is no evidence that treatment with an IGF inhibitory drug will cause patients to be immunosuppressed. Indeed, given experimental evidence that IGFs themselves can suppress the immune system, it is possible that treatment with xentuzumab could enhance immune responses. Therefore, we accept that extra hospital visits may confer additional COVID risk, but the treatment itself should not increase this risk.

Covid 19 Vaccination Considerations

There is no contraindication to having a COVID-19 vaccination before, during or after the study and participants will be encouraged to do so.

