5.1 Patient evaluability and replacement

The trial will be assessed on a modified intention-to-treat basis. Patients who are not evaluable for the primary endpoint may be replaced at the TMGs discretion, this includes:

- Patients who receive fewer than 3 doses of xentuzumab e.g. due to early withdrawal
- Patients who for any reason do not have their planned standard of care prostatectomy
- Patients whose prostatectomy reveals predominantly neuroendocrine/small cell cancer
- Patients from whom diagnostic biopsy or surgical specimens were not taken or were of insufficient quantity or quality for analysis.
- Patients who do not receive their planned standard of care prostatectomy within 6 days of their final dose of xentuzumab.

If patients miss a dose(s) for unavoidable reasons (e.g. participants with covid infection or unable to attend for treatment in the scheduled visit window) they can remain on the trial provided they resume weekly dosing with the final dose of xentuzumab within 6 days of surgery.
All participants who receive one or more doses of xentuzumab will be evaluable for safety analysis.

As noted above, patients withdrawing early after one or more doses of xentuzumab, irrespective of their stage in the trial, will undergo evaluations on the day before surgery.

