8.2 Concomitant medication and non-drug therapies

Concomitant medication may be given as medically indicated. All patients will be asked to provide a complete list of prescription and over-the-counter medications that have been taken within the previous 4 weeks prior to the first treatment visit. They must also inform the Investigator about any new medication started while on the trial.

Details must be recorded in the medical record and the appropriate CRF including indication, doses, frequency and start/stop dates) of concomitant medication taken during the trial until the completion of the off-study visit.

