## 2 BACKGROUND AND OBJECTIVES

WINGMEN is a windows trial of IGF blockade pre-prostatectomy. The aim is to identify key IGF-regulated genes/proteins that mediate effects of high serum IGF-1 in driving prostate cancer risk and progression.

The estimand for the primary objective (including the analysis of the primary outcome) is described in Table 1. This trial is unusual in that it lacks a control arm. Patients serve as their own control through collection of samples before xentuzumab treatment. This affects the way intercurrent events are handled.

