#### 4.1.3 Research/translational endpoints producing single values

Exploratory analyses will be conducted using various statistical tests as appropriate for the data type. These include, but are not limited to, the following.

For endpoints which produce a single value PRE/POST xentuzumab (e.g. circulating biomarkers such as insulin, PSA, PMBC immunotypes; IGF bioactivity; exploratory tissue biomarkers) paired t-tests or Wilcoxon rank sum tests will be used to assess the significance of differences pre and post treatment. Which test will be used will be determined by the results of the Shapiro-Wilk test for normal distribution. For unpaired data, either unpaired t-tests or the Mann-Whitney U test will be used, again depending on results of the Shapiro-Wilk test for normal distribution. These results will be presented and analysed as for primary endpoint markers and as shown in WINGMEN\_DataDefinitions&Tables Section 5. Results will be displayed as either the mean (and standard deviation), or median (with lower and upper quartiles).

Relationships between many of these variables may be assessed for correlation. The Pearson correlation coefficient  $r$  will be used where two sets of raw data show a linear relationship with one another. If the

relationship is monotonic (i.e. non-linear) the Spearman's rank test (correlation coefficient  $\rho$ ) will be used to analyse correlation between ranked data.

We had planned to assess changes in on-study serum IGF-1, previously reported to rise in patients on xentuzumab reflecting hypothalamic-pituitary axis response to blockade of pituitary IGF-1R [6]. However, on-treatment serum IGF-1 values fell in WINGMEN trial subjects, and we found this was due to interference by xentuzumab in the IGF-1R assay used in the Biochemistry laboratory of the John Radcliffe Hospital.

Other research endpoints (e.g. RNA-seq, metabolomics) will generate larger datasets and will be handled using the methods described below.

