#### 6.6 Harms

*Provide sufficient detail on summarising safety data, e.g. information on severity, expectedness, and causality; details of how adverse events are coded or categorised; how adverse event data will be analysed, e.g. incident case analysis, intervention emergent analysis. Will adverse events/complications also be recorded, summarised and analysed – full details for reporting should be specified in the SAP – Data Definitions and Tables document.*

Potential harms include potential for drug toxicity and delay to standard of care surgery. Both will be captured as secondary endpoints and will be defined as described in WINGMEN\_DataDefinitions&Tables Section 2.2 and Table 2.

There is a risk of COVID-19 exposure and infection from trial-specific hospital attendances, but measures have been put in place to minimise this risk as far as possible. The WINGMEN recruitment site, Churchill Hospital, is

nominally COVID-19 free, and infected or potentially infected patients are treated at a geographically distinct site (John Radcliffe Hospital). The following procedures have also been put in place on site:

- All patients (in and outpatients) are screened upon entry to the Churchill site.
- Human traffic at the Churchill site is minimal, with face to face appointments avoided and staff working from home whenever possible.
- Face masks/social distancing/level 1 PPE for patient examinations and other protective measures are mandatory for staff at the Churchill site

Furthermore, this trial requires only 5 extra patients visits: screening and 4 treatment visits (unless surgery is unexpectedly delayed). The post-treatment End-of-Study trial assessment will be held on the same day as the routine 6-week post-operative assessment, and so will not involve an extra hospital visit. There is no evidence that treatment with an IGF inhibitory drug will cause patients to be immunosuppressed. Indeed, given experimental evidence that IGFs themselves can suppress the immune system [19, 20, 21], it is possible that treatment with xentuzumab could enhance immune responses. Therefore, we accept that extra hospital visits may confer additional COVID-19 risk, but the treatment itself should not increase this risk. There is no contraindication to having a COVID-19 vaccination before, during or after the study, and participants will be encouraged to do so if not already fully vaccinated.

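### The exploratory immune PRE/POST comparisons have no stated check for COVID-19 vaccination or infection between the two samples, so such effects could not be told apart from xentuzumab effects

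*Protocol*

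**What the plan says.** **Vaccination.** Protocol section 1.4 (Covid 19 Vaccination Considerations) states: "There is no contraindication to having a COVID-19 vaccination before, during or after the study and participants will be encouraged to do so". SAP section 6.6 repeats this in narrower form: "participants will be encouraged to do so if not already fully vaccinated". Neither places vaccination in time relative to the PRE and POST samples.

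**Infection.** Protocol section 5.1 gives as acceptable reasons for missed doses "participants with covid infection or unable to attend for treatment in the scheduled visit window", and says of these men that "they can remain on the trial provided they resume weekly dosing with the final dose of xentuzumab within 6 days of surgery". Section 7.4 repeats the rule.

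**Design and analysis.** SAP section 2 says "This trial is unusual in that it lacks a control arm". SAP section 4.1.3 applies paired t-tests or a Wilcoxon test, without adjustment, to endpoints with one value before and one after treatment: "circulating biomarkers such as insulin, PSA, PMBC immunotypes; IGF bioactivity; exploratory tissue biomarkers". SAP section 4.1.5 compares RNA-seq profiles and allows immune pathways to be picked by hand, depending on results such as the PBMC profiling.

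**Nearest safeguards.**
- Protocol 8.2 collects medications, with start and stop dates, from 4 weeks before the first treatment visit. It adds: "They must also inform the Investigator about any new medication started while on the trial". Vaccines are not named.
- Protocol 10.8 records adverse events with onset dates.
- SAP 5.5 records reasons for delayed cycles, and standardises the blood draw for time of day and meal interval.
- SAP Table 1 refers some intercurrent events to the Chief Investigator, within the estimand for the primary markers.
- SAP 6.3 (sensitivity analysis) deals with spare material, repeat assays and assay controls.

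**The concern.** Each man is his own only comparator. Anything that alters immune markers between his two samples enters the PRE/POST difference on the same footing as the drug. A vaccine dose and a viral infection are plausible examples, and the protocol expects both to be possible on study.

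The immune question is not peripheral to the science. Protocol section 1.4 describes a hypothesis that includes suppression of anti-tumour immunity by high IGF, and calls it the trial's focus. A shift caused by vaccination or infection could resemble the hoped-for result. It could also carry over, because PBMC findings may steer which gene sets are examined under SAP 4.1.5.

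At stake is the reading of the exploratory immune results: whether a change can reasonably be discussed as a xentuzumab effect.

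**Working it through.** **Plan figures.** The plan gives no figure for this point. Its sample-size figures concern the primary markers and are not in dispute. With effect size 0.68, 80% power and alpha 0.05, a noncentral-t calculation with Wilcoxon efficiency 3/π gives 20 pairs two-tailed (power 0.803) and 16 one-tailed (power 0.812), as stated. With effect size 0.6, the paired t calculation gives the 24 pairs in SAP 3.2. I use 24 pairs below.

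**Does any rule cover these events?**

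| Place | Content | Covers vaccination or infection for immune endpoints? |
|---|---|---|
| Protocol 4.1, 8.3 | Exclusions, prohibited therapies | Neither event is specifically listed |
| Protocol 14.2 | Subgroups: PTEN, serum IGF-1, IGF1 mRNA | No |
| SAP Table 1 | Chief Investigator review, no criteria | Primary markers only; the sentence on other endpoints breaks off in the text available |
| SAP 4.1.3, 4.1.5 | PRE versus POST tests | No adjustment, exclusion or rerun |
| SAP 6.3 | Repeat assays and controls | No |

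**How large could it be?** The documents give neither the number of affected men nor the size of any shift, so both are assumptions. Let k of n men have their change shifted by s, in SDs of the within-man change, with no drug effect.

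Bias in the mean change = k × s / n:
- k = 2, s = 1: 2 × 1 / 24 = 0.083 SD
- k = 4, s = 1.5: 4 × 1.5 / 24 = 0.25 SD

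False-positive rate per marker (simulation, 24 pairs, paired t, two-sided 0.05):

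| Affected men, shift | All shifts full, same direction | Shifts faded uniformly between full and zero | Direction random | Affected men excluded |
|---|---|---|---|---|
| 2 men, 1 SD | 6% | 5% | 5% | 5% |
| 4 men, 1.5 SD | 14% | 8% | 5% | 5% |

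The Wilcoxon signed rank test gives similar figures (6% and 12%).

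**How many men might be affected?** Suppose, as an assumption only, one vaccine dose every 6 to 12 months at random times, and a window of 24 to 42 days (the planned day of surgery). The share caught is 24/364 = 6.6% to 42/182 = 23.1%, which is 1.6 to 5.5 of 24 men. The SAP's restriction to men not fully vaccinated would lower this. A seasonal campaign, infections or delayed surgery would raise it. For tissue the window is longer, because the PRE sample is the diagnostic biopsy, taken before day 1.

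**Cost of excluding men.** If 4 of 24 are dropped, interval width grows by √(24/20) = 1.095, about 10%.

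**The case against.** The strongest reply has four parts.

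1. **Some governing text is not available.** The SAP is to be read together with a Data Definitions and Tables document, which holds the analysis populations, the exploratory analyses and the reasons for sample unsuitability. A rule could sit there, and the Table 1 sentence on other endpoints is incomplete. This stands: the point is limited to what the protocol and SAP contain.

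2. **The magnitude is assumed.** This also stands. One or two affected men barely move the test, and fading or mixed-direction shifts reduce the effect. A reader might infer a much worse case: 6 of 24 men (25%) with a 2 SD shift gives about 39%. But 25% lies above the 7–23% share worked out above, and nothing in the documents supports a shift of that size, least of all inside the prostate.

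3. **The endpoints are exploratory.** True, and it limits the weight of the point. It does not remove it, because following SAP 4.1.3 as written leaves the ambiguity in the reported result.

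4. **The data are already collected, and other immune exposures raise the same issue.** The first part makes the remedy cheap. The second is fair (corticosteroids are allowed for infusion reactions, for example), but vaccination is the exposure that the plan itself encourages.

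**Conclusion.** The gap is real but modest. In the protocol and SAP, an effect of vaccination or infection between PRE and POST cannot be distinguished from an effect of xentuzumab on the exploratory immune endpoints. Its size is unknown. The 6% to 14% range rests on 24 pairs, no drug effect, 2 to 4 affected men and full shifts of 1 to 1.5 SD in one direction.

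Three stronger readings are not supported:
- **That such effects will be reported as drug effects.** This depends on how many men were affected, which the documents do not say; it may be none.
- **That the primary result is compromised.** Nothing here shows an effect on phospho-IGF-1R or phospho-S6, or on the sample size.
- **That removing affected men makes the remaining change attributable to the drug.** It removes one alternative explanation; the comparison is still uncontrolled.

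**What to change.** Leave the vaccination and dosing policy unchanged. SAP 3.4.4 says recruitment was complete by Q1 2023 and SAP v1.0 is dated June 2024, so new CRF fields would come too late. Work from existing records.

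If the Data Definitions and Tables document has no such rule, add one there or in SAP 4.1.3 and 4.1.5:

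- From the concomitant-medication, adverse-event and delayed-cycle records, report how many men had a vaccine dose or documented SARS-CoV-2 infection between their PRE and POST samples. For tissue, count from the diagnostic biopsy as far as records allow. Medication history reaches back only 4 weeks before first treatment, and adverse-event recording starts at consent, so state any uncovered interval.
- As a pre-specified sensitivity analysis, repeat each immune endpoint without those men: PBMC immunophenotypes, tissue CD4, CD8, FoxP3 and PD-L1, and any immune gene sets selected.
- Show both estimates with intervals. Compare the estimates, not whether p crosses 0.05, since the smaller set has less power.
- State that an immune change not seen in the sensitivity analysis cannot be attributed to xentuzumab.

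The cost is one paragraph, a review of existing records and one rerun per immune endpoint, with the wider intervals shown above in the supportive analysis only. If no man was affected, saying so removes the alternative explanation.

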2 TRIAL DESIGN

This is an open label, 'window of opportunity' study investigating whether xentuzumab inhibits IGF signalling and proliferation in patients with localised prostate cancer scheduled for radical prostatectomy. The study is a Phase 0 trial because of the window of opportunity design where treatment-naïve patients are exposed to agent for a very short period of time, and the endpoints are related not to disease outcome but rather to provide a within-patient comparison to quantify IGF axis inhibition and identify mediators of high IGF supply that promote cancer progression. Thirty participants will be recruited at a single trial centre (Oxford University Hospitals NHS Foundation Trust).

Following successful completion of screening, participants will receive 4 weekly intravenous doses of xentuzumab prior to their standard of care prostatectomy, at which samples will be collected for comparison with the participant's diagnostic biopsy. Participants whose surgery is early, may receive only 3 doses, equally if surgery is delayed participants can receive up to 10 xentuzumab doses, patients must receive their prostatectomy within 6 days of their final dose of xentuzumab to be evaluable. Refer to the schedule of events and flow chart for details of the study visits and procedures.

2.1 Duration of patient participation

Participants will be in the study for approximately 12 weeks (if surgery is not delayed) from start of screening to the last follow-up protocol visit 6 weeks after surgery.

2.2 Post-trial care and follow-up

Following radical prostatectomy an end of study visit will be completed and patients will receive standard care.

4 PATIENT SELECTION

Written informed consent must be obtained before any study specific procedures are performed. The Investigator will determine patient eligibility based on the following criteria. Men with localised prostate adenocarcinoma who are due to undergo a radical prostatectomy will be identified through information provided from the medical records at the weekly Urology Multi-Disciplinary Team (MDT) meeting. An additional check will be made at the MDT to assess the tumour content of the diagnostic biopsy, to ensure that patients are approached only if they have sufficient diagnostic biopsy material, surplus to diagnostic need, for the primary endpoint analysis.

Patients in this study may be co-enrolled on the TRANSLATE diagnostic trial comparing Local Anaesthetic Transperineal biopsy (LATP) to Transrectal Ultrasound (TRUS) biopsy of the prostate. TRANSLATE has a 4-month follow up period and would therefore overlap with the WINGMEN trial. Men will be approached about the TRANSLATE trial before their diagnostic biopsy; those who are subsequently found to be suitable for radical prostatectomy surgery will be approached about the WINGMEN study. Follow-up data collection for men co-enrolled to the TRANSLATE trial would continue; patients co-enrolled in the TRANSLATE trial would still receive questionnaires to complete (relating to Health-Related Quality of Life, symptom, and biopsy-related outcomes) at 7 days, 35 days and 4 months post-biopsy, to complete their post-biopsy follow up. This should not be too burdensome for the patients, and would not compromise recruitment to the WINGMEN study.

4.1 Eligibility criteria for entry into the study

Inclusion criteria:

A patient will be eligible for inclusion in this study if all of the following criteria apply.

1. Men with prostate adenocarcinoma confirmed on prostate biopsy and with sufficient cancer-containing biopsy tissue surplus to diagnostic need to provide ≥ 2 sections for primary endpoint analysis.
2. Scheduled for open or robotic radical prostatectomy
3. Age ≥ 18 years
4. Eastern Cooperative Oncology Group (ECOG) performance status 0 or 1 (Appendix 1)
5. The patient is willing and able to comply with the protocol scheduled follow-up visits and examinations for the duration of the study
6. Participant is willing and able to give informed consent.
7. Participants whose partner is of child bearing potential must be willing to ensure that they or their partner use effective contraception during the trial and for 70 days thereafter.
8. Adequate haematologic, renal and hepatic function, defined as follows:

Laboratory Test	Value required
Haemoglobin (Hb)	≥ 90 g/L

White Blood Count (WBC)	>2.5 x 10 ⁹ /L
Absolute Neutrophil Count (ANC)	≥ 1.5 x10 ⁹ /L
Platelet count	≥ 100 x 10 ⁹ /L
AST, ALT, and alkaline phosphatase	≤ 2.5 x upper limit of normal
eGFR*	≥30ml/min

*eGFR calculated by Cockcroft & Gault formula, see appendix 2

Exclusion criteria:

A patient will not be eligible for the trial if any of the following apply:

1. Treated with systemic corticosteroids, insulin, metformin, other oral hypoglycemic agent, or anti-androgens in the 28 days prior to first dose of study drug
2. Diabetes mellitus
3. Previous prostate radiotherapy
4. Current or previous treatment with xentuzumab or other IGF or GH -modifying therapy
5. Patients who are known to be serologically positive for Hepatitis B, Hepatitis C or HIV
6. Treatment with any other investigational agent, or treatment in another interventional clinical trial within 28 days prior to enrolment
7. Other psychological, social or medical condition, physical examination finding or a laboratory abnormality that the Investigator considers would make the patient a poor trial candidate or could interfere with protocol compliance or the interpretation of trial results.

4.2 Protocol deviations and waivers to entry criteria

A trial related deviation is a departure from the ethically approved trial protocol or other trial document or process (e.g. consent process or IMP administration) or from Good Clinical Practice (GCP) or any applicable regulatory requirements.

Protocol adherence is a fundamental part of the conduct of a clinical study. Changes to the approved protocol need prior approval unless for urgent safety reasons.

Investigators must contact OCTO to obtain guidance and/or clarification as necessary if unsure whether the patient satisfies all the entry criteria and to clarify matters of clinical discretion. OCTO will contact the chief investigator or clinical coordinators as necessary. Investigators should not request a protocol waiver to enter a patient who does not satisfy the selection criteria.

The investigator must document and explain any deviations/violations from the approved protocol. The investigator should promptly report any important violations that might impact patient safety, data integrity or be a possible serious breach (see 19.7 below) to the trial office.

